3.2. Blinding/Unblinding

This is an open-label, non-randomized study. Blinding/unbinding is not applicable.

3.3. Determination of Sample Size

A total of approximately 115 patients will be enrolled in the study.

Approximately 60 patients with solid tumors harboring *FGFR* rearrangements will be enrolled in Cohort A. Sample size considerations (primary endpoint ORR) are based on a 2-stage Simon design (Simon, 1989), comparing a poor response of $\leq 10\%$ vs a promising response of $\geq 25\%$, at a 5% 1-sided significance level and approximate 90% power.

- In Stage 1 (futility assessment), enrollment will include 35 patients and accrual will continue to Stage 2, if at least 4 (11.4%) of 35 patients respond (CR or PR).
- In Stage 2, if the Stage 1 futility boundary is exceeded, an additional 25 patients will be enrolled, for a total of approximately 60 patients. With a total of 60 patients, if the observed ORR is 30%, the 95% exact confidence interval (CI) is 18.9%, 43.2%.

Table 3: Observed ORR with Exact 95% CI (Cohort A)

ORR	95% Exact Confidence Interval
20%	[10.8% - 32.3%]
25%	[14.7% - 37.9%]
30%	[18.9% - 43.2%]

Approximately 35 patients with gastric or GEJ cancer harboring *FGFR2* amplification will be enrolled in Cohort B. Sample size considerations are based on differentiating a historical control ORR of 10% or less, with a target ORR of 35%. Assuming the true ORR is 35%, the cohort has approximately 96% power to reject the null hypothesis that the true ORR is $\leq 10\%$, considering a 2-sided alpha of 5%. With a sample size of 35, observing at least 8 responders will have a 95% CI lower bound excluding 10% (ORR of 23% with 95% CI [10.4% - 40.1%]).

Table 4: Observed ORR with Exact 95% CI (Cohort B)

ORR	95% Exact CI
23%	[10.4% - 40.1%]
29%	[14.6% - 46.3%]
37%	[21.5% - 55.1%]

Approximately 20 patients with MLNs harboring *FGFR1* rearrangements will be enrolled in Cohort C. Sample size considerations are based on differentiating a historical control CR rate of 10% or less, with a target CR rate of 50%. Assuming the true CR rate is 50%, the cohort has over 95% power to reject the null hypothesis that the true CR rate is $\leq 10\%$, considering a 2-sided alpha of 5%.

Observing at least 6 responders out of 20 treated patients will have a 95% CI lower bound excluding 10% (CR rate of 30% with 95% CI [11.9% - 54.3%]).

Table 5: Observed CR Rate with Exact 95% CI(Cohort C)

CR Rate	95% Exact Confidence Interval
30%	[11.9% - 54.3%]
40%	[19.1% - 64.0%]
50%	[27.2% - 72.8%]

3.4. Interim Analysis

The Sponsor will review the data at the time Cohort A has 35 evaluable patients for ORR to determine if that particular cohort should continue.

4. STUDY PERIODS AND POPULATIONS FOR ANALYSIS

4.1. Study Periods for Analyses

Study periods are defined in [Table 6](#) and shown in [Figure 2](#).

Table 6: Definition of Study Periods for Analysis

Period	Definition
Screening Period (Baseline)	The Screening Period is defined as the time from when the patient signs the Informed Consent Form (ICF) until the date of first dose of futibatinib.
Treatment Period	The treatment period is the time from first dose of futibatinib (Day 1) to the date of last dose of futibatinib.
Safety Assessment Period	The Safety Assessment Period begins at the time the ICF is signed and continues until at least 30 days after the last dose of futibatinib.
On-treatment Period (This period will be used for safety analyses)	On-treatment Period is the time from the first dose of futibatinib (Day 1) to 30 days after the last dose of futibatinib. Unless otherwise specified, the On-treatment Period will be the basis for safety analyses.

[figure not shown]

Figure 2: Study Periods for Analysis

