9. SAFETY EVALUATIONS

9.1. Adverse Events

An AE is defined as any untoward medical occurrence in a clinical study patient and does not necessarily have a causal relationship with the study drug. An AE can therefore be any unfavorable and unintended sign (including an abnormal finding), symptom, or disease temporally associated with the use of a study drug, whether or not related to the study drug. This includes any occurrence that is new in onset or aggravated in severity or frequency from the baseline condition, or abnormal results of diagnostic procedures, including laboratory test abnormalities. For this study, progression of the cancer under study is not considered an AE unless the Investigator deems it related to study drug.

All AEs will be collected from the time informed consent has been documented through 30 days after the last dose of any study drug (safety follow-up) or until the start of new antitumor therapy, whichever is earlier. Any untoward medical event that occurs after the safety follow-up is not considered an AE, unless the Investigator considers that the AE is related to the study drug.

Signs and symptoms of a preexisting disease should not be considered an AE, but should rather be considered baseline signs and symptoms. Clinically significant worsening of preexisting signs and symptoms is considered an AE.

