9.4.2. Reporting of Serious Adverse Events (within 24 hours)

All SAEs occurring from the time informed consent has been documented through the Safety Follow-up Visit (30 days after the last dose of study drug or discontinuation, whichever is earlier) must be reported to Sponsor's Pharmacovigilance group or its designee immediately and no later than 24 hours from the time the Investigator first becomes aware of the SAE.

Comprehensive information available at the time of initial reporting (including narrative description, medical history, and concomitant medications) needs to be provided with careful consideration regarding causality and serious criterion. The SAE reporting process and contact information are provided in supplement guidelines.

After the initial SAE notification to the Sponsor's Pharmacovigilance group or its designee, all follow-up SAE information will be submitted each time they become available (for example, clinical diagnosis, outcome, causality assessment, or results of specific investigations) on a follow-up SAE form.

Investigators are not obligated to actively seek SAEs after the 30-day Follow-up. However, if the Investigator learns of any SAE (including a death) at any time after a participant has been discharged from the study, and the investigator considers the event to be reasonably related to the study treatment or participation, the investigator must promptly notify the Sponsor.

The Investigator also must submit further information if it is required by the Sponsor or the director of the study site or an institutional review board (IRB)/independent ethics committee (IEC).

Every SAE should be followed until it has resolved, stabilized, or returned to baseline.

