5.6.2.2. Adverse Events

An AE is any untoward medical condition that occurs in patients while participating in this clinical trial. AEs will be coded according to the MedDRA (the most up-to-date version at the time of analysis) terminology and the severity of the toxicities will be graded according to NCI CTCAE Version 5.0, where applicable.

A treatment-emergent AE (TEAE) is defined as an AE that is starting or worsening at the time of or after the first dose of study drug administration and within 30 days after the last dose of study drug, and does not necessarily have a causal relationship to the use of the study drug.

In this study, only TEAEs will be summarized. Note that all collected AEs, including TEAEs, will be presented in listings as described in Section 5.1.

The following summary tables will be generated:

1. Summary of AEs with the number and percentage of patients reporting AEs, serious AEs, grade ≥ 3 AEs, AEs leading to study drug discontinuation, interruption and dose reduction, and AEs with the outcome of death.
2. Summary of treatment-related AEs with the number and percentage of patients reporting AEs, serious AEs, grade ≥ 3 AEs, AEs leading to study drug discontinuation, interruption and dose reduction, and AEs with outcome of deaths.
3. Summary of AEs by worst CTC Grade (grade 1, 2, 3, 4, 5, any grade, Grade ≥ 3) presented by SOC and Preferred Term (PT).
4. Summary of TEAEs by worst CTC grade (Grade 1, 2, 3, 4, 5, any grade, Grade ≥ 3) presented by SOC and PT.
5. Grade ≥ 3 AEs by worst CTC Grade (grade 3, 4, 5, 3-5) presented by SOC and PT.
6. Grade ≥ 3 TEAEs by worst CTC Grade (grade 3, 4, 5, 3-5) presented by SOC and PT.
7. Summary of AEs leading to death by SOC and PT.
8. Summary of the most common AEs ($\geq 10\%$ incidence) and median time to first AE by SOC and PT.

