7.2. Post-Baseline Period

To allow differentiation as to which study period an AE occurred, three categories are defined based upon onset date. AEs that have onset dates prior to the first dose of study drug are considered "prior." AEs with onset dates on or after the first dose of study drug and within 30 days following the last dose of study drug are considered "on-treatment" or equivalently "treatment emergent.". Events with onset dates more than 30 days after the last dose of study drug are considered "post-treatment." No "subtracting rule" will be applied when an AE occurs both pre-treatment and post-treatment with the same preferred term and grade. AE summary tables will be based on on-treatment AEs only. AEs with onset dates prior to the first dose of study drug as well as those after the last dose of study drug +30 days will be identified in the data listings.

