7.4. Time-to-Onset Definition

Time-to-onset of AESI (any grade) for a specific category (for example, pulmonary events, gastrointestinal events) is defined as the time between the day of the first dose of study drug and the onset date of the earliest AESI (of any grade) in this category.

If the patient did not experience an AESI (of any grade) in the category, time-to-onset will be censored at the maximum follow-up time of that patient (that is, for patients without an event,

time-to-onset will be censored at last dosing date +30 days if patients are off treatment and followed for at least 30 days, otherwise it will be censored at the last known alive date.). If patients experience AESI for a specific category but with event start date after the last dosing date +30 days, time-to-onset will be censored at last dosing date +30 days. The resulting Kaplan–Meier plot will represent the cumulative rate of the AESI (any grade) in the category over time.

Time-to-onset of AESI (Grade 3-5) for a specific category is defined similarly but restricted to Grade 3-5 AESI.

Time-to-onset of drug-related (Grade 3-5 or any grade) AESI for a specific category is defined similarly but restricted to drug-related AESIs.

Time-to-onset for a specific subcategory is defined similarly but restricted to events in this subcategory.

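### SAP 7.4 keeps early switchers in the risk set for AESI time-to-onset after the protocol has stopped collecting their adverse events

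*SAP*

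**What the plan says.** **SAP.** Section 4.1 defines the safety window: "On-treatment Period is the time from the first dose of futibatinib (Day 1) to 30 days after the last dose of futibatinib". It also makes this the default: "Unless otherwise specified, the On-treatment Period will be the basis for safety analyses". The TEAE definition in 5.6.2.2 and the onset classification in 7.2 ("AEs with onset dates on or after the first dose of study drug and within 30 days following the last dose of study drug") use the same 30-day limit. For AESIs, Section 7.4 sets this rule where none has occurred: "time-to-onset will be censored at last dosing date +30 days if patients are off treatment and followed for at least 30 days"; all other event-free patients are censored at the last known alive date. None of these sections mentions new anticancer therapy.

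**Protocol.** Section 9.1 collects AEs "through 30 days after the last dose of any study drug (safety follow-up) or until the start of new antitumor therapy, whichever is earlier". The AE monitoring entry in Section 6 has the same stop at new therapy. Section 3.3.3 asks that the 30-day safety visit be held ahead of any new therapy begun within 30 days of the last dose. For serious events, Section 9.4.2 covers "All SAEs occurring from the time informed consent has been documented through the Safety Follow-up Visit", with a 30-day gloss in parentheses. Section 9.4.3 treats deaths in a similar way, by reference to the Safety Follow-up Period. Amendment 1 has the same AE stop, so the mismatch does not arise from the SAP following an older protocol.

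**The concern.** A Kaplan-Meier estimate of time to first AESI assumes that a patient in the risk set would have had the event recorded had it occurred. After new therapy starts, the protocol no longer routinely collects AEs, yet SAP 7.4 keeps the patient in the risk set. Risk time without ascertainment enlarges the denominator and adds few or no events, so the cumulative AESI rate comes out too low. The SAP applies this to selected AESIs such as hyperphosphatemia, for any grade and for Grade 3 or higher. What is at stake is the accuracy of descriptive safety curves.

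**Working it through.** The plan states no figure that bears on this point, so there is nothing to reproduce. The check is a comparison of rules, followed by an illustration of size.

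**Step 1: one patient under both rules.** Last dose is Day 0, new anticancer therapy starts on Day 10, there has been no AESI so far, and the patient is then in survival follow-up (protocol 3.3.5).
- Protocol 9.1 and Section 6: AE collection ends on Day 10.
- SAP 7.4, first branch: off treatment and followed for 30 days, so censored event-free on Day 30. This gives 30 - 10 = 20 days of credited but unobserved time.
- SAP 7.4, second branch: if being followed is taken to mean followed for AEs, the patient falls to the last known alive date. A patient who starts new therapy is alive on that day, so this date cannot precede the switch. In survival follow-up it may lie well beyond Day 30.

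Neither branch censors at the point where collection stopped.

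**Step 2: size, on assumptions.** Let f be the share of patients starting new therapy within 30 days of last dose, d the day of that start, and T the mean days on treatment. None of these is in the documents. The assumed ranges are f = 10%, 25%, 50%; d = 7, 14, 21; T = 60, 120, 180.

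- Unobserved person-days = N x f x (30 - d)
- Share of the 30-day tail = f x (30 - d) / 30
- Share of the whole window = f x (30 - d) / (T + 30)

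| Case | Person-days, N = 100 | Share of tail | Share of whole window |
|---|---|---|---|
| f = 10%, d = 21, T = 180 | 100 x 0.10 x 9 = 90 | 0.9/30 = 3.0% | 0.9/210 = 0.4% |
| f = 25%, d = 14, T = 120 | 100 x 0.25 x 16 = 400 | 4/30 = 13.3% | 4/150 = 2.7% |
| f = 50%, d = 7, T = 60 | 100 x 0.50 x 23 = 1150 | 11.5/30 = 38.3% | 11.5/90 = 12.8% |

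**Step 3: limits of the illustration.** The formulas treat every patient as event-free to the end of the window, whereas patients leave the risk set at their first AESI. They also use the first branch of SAP 7.4; under the second, unobserved time is not capped at 30 - d days. A share of risk time is not itself the bias in the curve, which also depends on when AESIs occur.

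**The case against.** **A fixed 30-day window is a recognised, inclusive choice.** It is compatible with the protocol's Safety Assessment Period (3.3), which runs to at least 30 days after last dose, and counting every death in that window is conservative. This stands for the TEAE and death tables. It does not rescue the AESI censoring, where the question is whether the patient was still being observed.

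**The AESI onset analysis is descriptive, and some late events can still be recorded.** There is no hypothesis test, and protocol 9.1 still admits later events that the investigator considers related to study drug. Both points hold. They limit the consequence but do not restore routine collection.

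**A reader might infer more:** that all TEAE and SAE tables are contaminated by toxicity of the next treatment. The documents do not support that.
- If AE collection stops at the switch, ordinary AEs of the next therapy are not in the database to be tabulated.
- The AE summaries in SAP 5.6.2.2 to 5.6.2.5 are mainly counts and percentages of patients. They carry no risk time and do not change if later AEs are not collected. The exposure-adjusted rates in SAP 5.6.2.7 use total exposure time, and the SAP does not say whether this includes the 30-day tail.
- Protocol 9.4.2 and 9.4.3 run to the safety visit or safety period, which 3.3.3 moves ahead of new therapy. After that visit, 3.3 and 3.3.3 provide for assessing only drug-related SAEs, in patients who have not started new therapy. SAEs under the next therapy enter only if the parenthetical 30 days is read as fixed.
- Nothing in the documents shows that switching speed differs by cohort.

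**What remains of that reading concerns deaths.** Survival follow-up captures deaths whatever happens to AE collection, and SAP 5.6.2.1 summarises those that are on-treatment. One death under new therapy within 30 days would add 1/100 = 1 point in Cohort A, 1/35 = 2.9 points in Cohort B and 1/20 = 5 points in Cohort C. The documents give no basis for expecting any particular number. Reasons for death are tabulated and all deaths are listed, which already helps with attribution.

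**Conclusion.** The concern holds for the AESI time-to-onset analysis. SAP 7.4 censors event-free early switchers after the protocol has stopped collecting their AEs, and under either branch of the rule the direction is downward. The size cannot be determined from the documents. Over the whole at-risk window it is probably small: about 0.4% to 13% of risk time under the assumed switch shares, switch days and treatment durations, and 2.7% in the middle case.

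The wider TEAE and death window is a defensible convention and need not be shortened. It may include deaths, and on one reading of protocol 9.4.2 SAEs, that occur under the next therapy. That is a possibility to be made visible, not an established upward bias.

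**What to change.** 1. In SAP 7.4, censor AESI time-to-onset at the earliest of last dose + 30 days, the start of new anticancer therapy and the last known alive date. Extend the existing rule for AESIs starting more than 30 days after last dose so that those starting after new therapy are also censored.
2. Keep the fixed 30-day window in SAP 4.1, 5.6.2.2 and 7.2 for the TEAE and death tables. Flag deaths, and any SAEs, with onset after new therapy started.
3. Reconcile the collection stops in protocol 9.1, 9.4.2, 9.4.3 and 3.3.3, so that it is clear whether SAE and death reporting ends at the brought-forward visit or at a fixed 30 days.

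The SAP part is wording only. Dates of subsequent therapy are already needed: protocol 3.3.5 records later anticancer treatments, and SAP Tables 10 and 12 censor PFS and DOR on them. The cost is slightly less follow-up time in the AESI onset curves; an AESI recorded after an early switch would appear only in the tables and listings.

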4.2. Populations for Analysis

The analysis populations in the study are defined in [Table 7](#).

Table 7: Definitions of Analysis Populations

Analysis Population	Definition
All Enrolled Population	All patients who signed the ICF in this study
All Treated Population/Full Analysis Set	All enrolled patients who received at least 1 dose of study drug
Pharmacodynamic/Biomarker Evaluable Set	All patients in the All Treated Population who have evaluable pharmacodynamic/biomarker data for analyses

As described in Section 5.5.1.1 and Section 5.5.1.2, DOR, duration of CR, duration of CR+CRi, RFS, and EFS will be analyzed using appropriate sub-populations of the All Treated Population.

4.3. Timing of Analysis

The Sponsor will review the data of Cohort A in order to determine if the Cohort A should continue or not when 35 patients (All Treated Population) in Cohort A have completed at least 6 months follow-up.

The final analysis will be performed when all patients either discontinue from the study or have sufficient follow-up (at least 6 months) from the first dosing date of futibatinib of the last enrolled patient, whichever comes first.

5. STATISTICAL ANALYSIS

5.1. General Methods

Other than exploratory biomarker data, which will be treated differently as explained above, all recorded data will be presented in listings. Data listings will be presented with patient ID and cohort.

Summary tables will be presented for each cohort.

The categorical data will be summarized using frequency counts and percentages of patients, unless otherwise specified.

The continuous data will be summarized using the number of non-missing observation (n), mean, standard deviation, median, minimum value, and maximum value, unless otherwise specified.

Prior anticancer therapy and concomitant medications will be coded with the WHO Drug Dictionary (the most up-to-date version at the time of analysis) and will be summarized by Anatomical Therapeutic Chemical (ATC) Classification level 2 (Therapeutic Main Group) and ATC level 4 (Chemical/Therapeutic Subgroup). Medications and therapies will be sorted in descending order of frequency of ATC level 2 and ATC level 4 within ATC level 2 in the total column. A patient will be counted only once within each level of summarization if the patient has taken a medication more than once. Agents and medications will be reported using the generic name.

For concomitant medications/therapy and adverse events (AEs), the cycle number is determined based on their start/onset dates. For other collected data, the cycle number is determined based on their visit dates. These data include a safety lab test, physical examination, vital signs, weight, ophthalmological exam, Eastern Cooperative Oncology Group (ECOG) performance status (PS), electrocardiogram (ECG), pregnancy test, and scheduled tumor assessment.

If there are multiple laboratory records for a scheduled visit, the one closest to the target date will be used for analysis. If there are two or more records with the same time period to the target date, the record with the latest database entry date will be used for analysis.

CIs for binomial proportions (eg, ORR and DCR) will be derived using the Clopper–Pearson method.

Time to event distribution (eg, PFS, OS, and DOR) will be estimated using the Kaplan–Meier method. The number of events and censorings will be reported. When appropriate, the median along with the corresponding log-log transformed 95% CI will be estimated. Survival rates at fixed time points will be derived from the Kaplan–Meier estimate and the corresponding CI will be derived based on the Greenwood formula for variance derivation and on log-log transformation applied on the survivor function $S(t)$.

All the analyses for this study will be performed using SAS[®], Version 9.3 or a higher version.

5.2. Study Conduct

5.2.1. Accrual

For All Enrolled Population, the number of patients accrued, will be summarized by country and investigational site for each cohort.

5.2.2. Protocol Deviations

For the All Enrolled Population, important protocol deviations will be summarized by category for each cohort. An important protocol deviation (ICH E3 Q&A [R1]) is defined as a subset of protocol deviations that may significantly impact the completeness, accuracy, and/or reliability of the study data or that may significantly affect the patient's rights, safety or well-being. These include important informed consent form (ICF) issues, inclusion/exclusion criteria not met, withdrawal criteria not followed; wrong treatment, incorrect dose/overdose based on protocol definitions, important deviations based on protocol design, and other important Good Clinical Practice (GCP) deviations.

According to US Food and Drug Administration (FDA) guidance on conduct of clinical trials of medical products during COVID-19 pandemic, updated on March 27, 2020, protocol deviations related to COVID-19 will be listed in the CSR (FDA, 2020).

